7.2.2 Injection Site Assessments

Subjects will report any ISR to the eDiary. Subjects will describe the characteristics of the ISR (pain/tenderness, erythema/redness, induration/swelling, pruritus/itching, hematoma/ecchymosis/bruising) at the site of injection.

Study drug injection sites will be assessed by the site staff at each visit. Any findings (e.g., pain/tenderness, erythema/redness, induration/swelling,

pruritus/itching, hematoma/ecchymosis/bruising) will be recorded on the ISR worksheet and entered into the eCRF as an AE. The AE term “ISR” with the grade of AE consistent with the worst grade for any 1 of the findings should be reported. An additional eCRF will also be created to capture more detailed information regarding injection site reactions.

At the initial treatment visit (Week 0/Day 0), the subject will be asked to remain at the site for 2 hours after the initial injections in order to be monitored for ISRs and other AEs. At subsequent visits, all injection sites will be examined.

7.2.3 Weight, Height, Body Surface Area and Body Mass Index

Weight (kg) and height (cm) will be measured at Screening. Subjects should be weighed wearing indoor, daytime clothing with no shoes. Before being weighed, subjects should empty their bladders.

In addition, weight will also be measured at Week 24, 32, 40 and 48 and, if the subject discontinues study participation, at the ET visit 56 days (8 weeks) after the last dose of study drug.

Body Mass Index should be calculated at screening using the method below:

English Units: $BMI = \text{Weight (lb)} / (\text{Height (in)} \times \text{Height (in)}) \times 703$

Metric Units: $BMI = \text{Weight (kg)} / (\text{Height (m)} \times \text{Height (m)})$

A web based calculator can be found at the following URL:

http://www.nhlbi.nih.gov/health/educational/lose_wt/BMI/bmicalc.htm

Body surface area (m^2) should be calculated at Screening using the Mosteller formula ([Mosteller, 1987](#)):

$$BSA (m^2) = \sqrt{(\text{Ht in cm} \times \text{Wt in kg}) / 3600}$$

A web-based calculator using the Mosteller formula may be found at the following URL: www.halls.md/body-surface-area/bca.htm. Make sure that the Mosteller formula is used to calculate BSA as this website offers several formulas.

Percentage of BSA affected by chronic PsO should be roughly estimated by using the subject’s palm size as roughly 1% of the total BSA and the BSA by body area used to assess PASI:

- Head and neck ~10%
- Upper extremities ~20%
- Trunk ~30%
- Lower extremities + buttocks ~40%

7.2.4 Vital Signs

Vital signs will be collected at every visit and include blood pressure (obtained using arm or wrist cuff), heart rate, respiratory rate, and oral, aural, or axillary temperature and will be obtained at all study visits using a standardized process:

- The subject should sit for 5 minutes with feet flat on the floor and his/her measurement arm supported so that the midpoint of the manometer cuff is at heart level.
- A mercury sphygmomanometer or automatic blood pressure device with an appropriately sized cuff with the bladder centered over the brachial artery should be used (note: a wrist cuff centered over the radial artery is also acceptable).
- Blood pressure and heart rate should then be measured and recorded.

Blood pressure should be recorded to the nearest 2 mmHg mark on the manometer or to the nearest whole number on an automatic device.

7.2.5 **Electrocardiogram**

A 12-lead ECG will be performed at Screening, Randomization (Week 0/Day 0) and at Weeks 12, 24, 40 and 48 or, if the subject discontinues study participation before Week 48, at the ET visit 56 days (8 weeks) after the last dose of study drug. If the Screening ECG is obtained within 2 weeks before starting study drug, it does not have to be repeated at Randomization (Week 0/Day 0) and the Screening values will be used as Baseline values. If the 12-lead ECG was obtained within the 4 weeks prior to ET visit and the results were not abnormal and of clinical concern, it does not need to be repeated at that visit. The ECG will be performed after the subject has been in the supine position for at least 10 minutes, will include all 12 standard leads, and will be recorded at a paper speed of 25 mm/sec. Standard ECG parameters will be measured, including RR, PR, and corrected QT intervals, and QRS duration. All ECGs must be evaluated by a qualified physician (i.e., Investigator) for the presence of abnormalities. Any abnormalities of clinical concern to the qualified physician may be read by a consulting cardiologist, per the Investigator's decision.

7.2.6 **Safety Laboratory Tests**

Safety laboratory tests will be performed at Screening; Randomization (Week 0/Day 0); at Weeks 4, 8, 12, 16, 20, 24, 32, 40 and 48; and at the Follow-up visit or, if the subject discontinues study participation before Week 48, at the ET visit 56 days (8 weeks) after the last dose of study drug. If the Screening chemistry, hematology, and urinalysis are obtained within 2 weeks of starting study drug, they do not have to be repeated at Randomization (Week 0/Day 0), and the Screening values will be used as Baseline values. If the safety laboratory tests were obtained within the 4 weeks prior to the ET visit and the results were within the normal reference ranges or within the specified allowed range for the protocol (e.g., liver function test results within $2 \times \text{ULN}$), they do not need to be repeated at that visit.

7.2.7 **Chemistry**

Samples will be drawn for assessment of the following parameters: alkaline phosphatase; sodium; potassium; total protein; calcium; chloride; bicarbonate;

glucose; creatine phosphokinase; lactate dehydrogenase; alanine aminotransferase; aspartate aminotransferase; albumin; total, direct, and indirect bilirubin; blood urea nitrogen; creatinine; and uric acid.

7.2.8 Hematology

Samples will be drawn for assessment of the following parameters: hematocrit; hemoglobin, mean corpuscular hemoglobin, mean corpuscular hemoglobin concentration, mean corpuscular volume, red blood cell count, white blood cell count with differential, and platelet count.

7.2.9 Urinalysis

Urine will be collected for urinalysis, which will include assessment of the following parameters: pH, specific gravity, protein, glucose, leukocyte esterase, bilirubin, blood, nitrite, and ketones. A urine microscopic examination will be performed when there are any abnormalities on any of the following 3 dipstick results: leukocyte esterase, blood, or nitrite.

7.2.10 Other Laboratory Tests

HIV and Hepatitis Screening

All subjects will be tested for HBsAg, HBcAb, HCV antibodies (and RNA as appropriate), and HIV at Screening. If screening for HIV and hepatitis was done within 3 months prior to Screening, these test results may be used as Screening values.

In accordance with local regulations, an additional consent will be obtained for HIV testing. Notification of state and federal authorities, as required by law, will be the responsibility of the Investigator.

Tuberculosis Screening

All patients will be tested for TB at Screening using the QuantiFERON-TB Gold test. Patients with a positive QuantiFERON-TB Gold test may not participate. The QuantiFERON® TB Gold test can be repeated once using a fresh sample in subjects with an indeterminate result or low positivity (defined as QuantiFERON TB Antigen minus Nil value = 0.35 - 2 IU/mL); if the repeat test result is negative, the subject may participate in the study ([Raychaudhuri, Nguyen, Raychaudhuri, & Gershwin, 2009](#)). Additional TB testing utilizing the QuantiFERON-TB Gold test will be performed at Week 24 and at the Follow-up or ET visit 56 days (8 weeks) after the last dose of study drug as applicable, if a test has not been performed within the previous 3 months. Monitoring may be performed more frequently for regions with high incidence of TB or to evaluate signs and symptoms that might be due to TB. At Screening, a CXR obtained within the last 6 months should not demonstrate evidence of active or latent TB or any other active disease process. If during the study or at follow up visits, if a patient has a positive QuantiFERON-TB Gold test, a CXR should be obtained to confirm the diagnosis of TB.

Pregnancy Test

Urine pregnancy tests will be performed on women of childbearing potential at Screening, Randomization (Week 0/Day 0); at Weeks 2, 4, 8, 12, 16, 20, 24, 32, 40, 48 ; and at the Follow-up visit or, if the subject discontinues study participation before Week 48, at the ET visit 56 days (8 weeks) after the last dose of study drug.

Pregnancy Reporting

If the subject participating in the study becomes pregnant during the study or within 56 days of last dose of study drug, the Investigator should report the pregnancy to WCT Clinical Safety personnel within 24 hours of being notified. WCT Clinical Safety personnel will then forward the Exposure In Utero form to the Investigator for completion.

A subject who becomes pregnant while on study drug will immediately be withdrawn from study treatment and ET visit study procedures will be performed.

The subject should be followed by the Investigator until completion of the pregnancy. If the pregnancy ends for any reason before the anticipated date, the Investigator should notify the Sponsor. At the completion of the pregnancy, the Investigator will document the outcome of the pregnancy. If the outcome of the pregnancy meets the criteria for immediate classification as an SAE (i.e., postpartum complication, spontaneous abortion, stillbirth, neonatal death, or congenital anomaly), the Investigator should follow the procedures for reporting an SAE.

7.2.11 Anti-Drug Antibody Assessment

Antibodies to adalimumab will be measured in the sera of subjects enrolled in this study to compare the immunogenicity of CHS-1420 to that of Humira.

Immunogenicity will be evaluated over the course of the study. Comparison of immunogenicity will be made at Weeks 0/Day 0 (pre-dose), 2, 4, 8, 12, 16, 20, 24, 32, 40, 48 and at the ET or Follow Up visit 56 days/8 weeks after the last dose of study drug.

The immunogenicity testing will be performed using validated ECL ADA assays. Presence of ADA based on this confirmatory assay will be compared between groups. An assay to determine if ADAs are neutralizing may be used.

7.2.12 Highly Sensitive C-reactive Protein

Blood samples for measurement of hs-CRP will be collected for subjects with concurrent PsA at Randomization (Week 0/Day 0) and at Weeks 12, 16, 24, 40, 48 and the Follow Up Visit or, if the subject discontinues study participation before Week 48, at the ET visit 56 days (8 weeks) after the last dose of study drug. In this study, the hs-CRP (mg/L) is used as a marker of inflammation and not as a screening test for cardiovascular risk, and hs-CRP results will not be shared with the subject.

7.2.13 Serum Retention Samples

Serum samples will be collected from all subjects at Randomization (Week 0/Day 0) (pre-dose); at Weeks 2, 4, 8, 12, 16, 20, 24, 32, 40, 48 ; and at the Follow-up visit or, if the subject discontinues study participation before Week 48, at the ET visit 56 days (8 weeks) after the last dose of study drug. These serum samples may be used to evaluate AEs and serum adalimumab levels in conjunction with assessment of AEs, loss of response, or compliance; to correlate with ADA assay results; or to meet any other regulatory requirement. No other biomarkers or genetic testing will be performed on these samples. Samples will be retained at the Medpace Reference Laboratory until testing and unused samples and remnants or used samples will be destroyed 2 years after the study is completed (final database lock).

7.2.13.1 Sample Collection Procedures and Bioanalytical Methods

Instructions for sample collection and handling are included in the laboratory manual. All clinical laboratory evaluations should be performed at the same central laboratory. In the event that immediate laboratory analyses are required to assess an AE, a local laboratory may be used; however, a duplicate blood sample should also be sent to the central laboratory.

8 PLANNED ANALYSES

8.1 Analysis Populations

8.1.1 Randomized Population

The Randomized Population will include all randomized subjects. Subjects will be allocated to the treatment arm they are randomized to for a particular Treatment Period of analysis.

8.1.2 Full Analysis Population

The Full Analysis Population (FAP) will include all randomized subjects who receive 1 or more doses of study drug. The FAP is the primary efficacy analysis population. Subjects will be allocated to the treatment arm they are randomized to for a particular Treatment Period of analysis.

8.1.3 Safety Population

The Safety Population, like the FAP, will include all randomized subjects who receive 1 or more doses of study drug, but subjects will be allocated to the treatment arm based upon actual treatment received for a particular Treatment Period of analysis.

8.1.4 Per Protocol Population

The Per Protocol Population is defined as those subjects in the FAP completing at least 12 weeks of treatment and follow-up with respect to the PASI and have no protocol violations that may affect the interpretation of the primary efficacy endpoint. These violations will be identified by the Sponsor prior to study unblinding.

Subjects will be allocated to the treatment arm they are randomized to for a particular Treatment Period of analysis.

8.1.5 Open Label Extension Population:

The Open Label Extension Population is defined as those subjects receiving at least 1 dose of open label treatment. Subjects will be allocated to the treatment arm they received in Treatment Period 2.

8.2 Statistical Methods

8.2.1 Demographic and Baseline Characteristics

Descriptive summaries of demographic and Baseline characteristics at the time of randomization will be presented by treatment group. A detailed description of subject disposition will also be provided.

8.2.2 Efficacy Analysis

The primary statistical analyses will be based on:

- The difference between the percentages of subjects in the CHS-1420 and Humira groups achieving PASI-75 at Week 12.

Equivalence will be based upon the 95% (2-sided) confidence interval for the difference in PASI-75 rates. If both the lower and upper bounds of the 95% confidence interval exclude $\pm 15\%$ (inclusive), equivalence will be established. The mean percent change in PASI from Baseline to Week 12 between the CHS-1420 and Humira (US) groups will be assessed as a supporting secondary endpoint.

Subjects who lack a PASI assessment at Week 12 will be considered non-responders in the primary analyses. As a sensitivity analysis, the last available score will be used.

For PASI-75 at Week 12 (as well as for other binary outcomes where formal evaluations are made, if applicable), Cochran-Mantel-Haenszel weights will be used to combine the stratum specific differences ([LaVange, Durham, & Koch, 2005](#)) formed by the randomization strata.

For the percent change in PASI from Baseline (as well as for other continuous outcomes where formal evaluations are made, if applicable), the stratum-specific differences will be combined using an analysis of variance approach with weights proportionate to the stratum sizes.

Other secondary continuous variables will be summarized using descriptive statistics (N, mean, standard deviation, 95% confidence interval, median, minimum, and maximum) and discrete variables will be summarized using frequency counts and percentages.

For data collected after the start of Treatment Period 2, data summaries for efficacy will be presented by the particular treatment sequence received in Treatment Periods 1 and 2: CHS-1420/CHS-1420, Humira/Humira and Humira/CHS-1420.

For data collected during the open label extension, only descriptive data summaries will be presented. These summaries will be presented by the particular treatment received in Treatment Period 2, regardless of treatment received in Treatment Period 1.

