	
injection technique before administering study drug and on an electronic diary (eDiary), to track compliance and subject-reported ISRs. Subjects/caregivers will contact the eDiary following each injection to document dosing on the day of injection and any possible ISRs after the injection. During site visits, subject questionnaires will be completed by subjects using an electronic diary in the clinic.
 
The primary efficacy endpoint is the proportion of subjects achieving 75% improvement in Psoriasis Area and Severity Index (PASI-75) at week 12. The proportion of subjects achieving PASI-75 at 16 weeks will be a secondary efficacy endpoint.
 
An independent, unblinded Data Monitoring Committee will review Treatment Period 1 study data to determine if there is adequate safety and efficacy to warrant continuing the study to completion.
 
Subjects who discontinue study drug for any reason during Treatment Period 1 will be encouraged to return for all study visits through Week 16 if applicable and for the ET visit 56 days (8 weeks) after the last dose of study drug per the protocol Schedule of Procedures. Subjects who discontinue study drug for any reason during Treatment Period 2 or 3 will be encouraged to return for the Follow-up or ET visit 56 days (8 weeks) after the last dose of study drug (also per the protocol Schedule of Procedures). The Follow-up or ET visit will include evaluation of safety and immunogenicity (formation of anti-drug antibodies [ADAs]).

Study Centers	Approximately 160 active clinical sites worldwide will participate in this clinical trial.
Sample Size	The sample size determination is based on demonstrating a comparable PASI-75 at Week 12. Assuming that 70% of subjects in both the reference group, Humira, and the CHS-1420 group achieve PASI-75, with a statistical margin of 15% (absolute), approximately 250 subjects per treatment group will produce 90% power to establish equivalence at the 5% alpha level (2-sided) for the period 1 comparison. Subjects who lack follow-up data for the week 12 assessment will be considered non-responders in the primary analyses.
Study Population	Adult male and female subjects with moderate to severe chronic PsO.

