The first dose of study drug on Week 0/Day 0 will be self-administered or administered by a caregiver at the investigative site, and subjects will be monitored for adverse reactions and ISRs during the 2 hours after this dose. Subsequent doses will be self-administered or administered by a caregiver at home. Subjects/caregivers will be trained on injection techniques and the electronic diary (eDiary) used to track compliance and subject-reported ISRs. Subjects/caregivers will contact the eDiary following each injection to document dosing on the day of injection and any possible ISRs after the injection.

The primary efficacy endpoint is the proportion of subjects achieving 75% improvement in Psoriasis Area and Severity Index (PASI-75) at Week 12. When an adequate amount of data are available for the primary endpoint, an independent, unblinded Data Monitoring Committee (DMC) will review the accumulating safety and efficacy to determine if the data are adequate to warrant continuing the study.

Subjects who discontinue study drug for any reason during Treatment Period 1 will be encouraged to return for all study visits through Week 16 and for the ET visit 56 days (8 weeks) after the last dose per the protocol Schedule of Procedures, and subjects who discontinue study drug for any reason during Treatment Period 2 or 3 will be encouraged to return for a Follow-up or ET visit 56 days (8 weeks) after the last dose of study drug (also per the protocol Schedule of Procedures). This Follow-up or ET visit will include evaluation of safety and immunogenicity (formation of anti-drug antibodies [ADAs]).

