3.3.4 Removal of Subjects from Therapy

Subjects will be advised that they are free to withdraw from the study at any time for any reason; however, subjects who discontinue study drug for any reason prior to the end of Treatment Period 1 will be encouraged to return for all study visits through Week 16 and for an ET visit 56 days (8 weeks) after the last dose of study

drug per the protocol Schedule of Procedures (if applicable), and subjects who discontinue study drug for any reason during Treatment Period 2 or 3 will be encouraged to return for the Follow-up or ET visit 56 days (8 weeks) after the last dose of study drug (also per the protocol Schedule of Procedures). This Follow-up or ET visit will include evaluation of safety and immunogenicity (formation of ADAs).

Subjects may be withdrawn from study therapy for any of the following reasons:

- The subject experiences a serious adverse event (SAE) or medically important AE (e.g., serious or opportunistic infection) that would preclude further treatment with study drug;
- The subject develops a malignancy while on study;
- The subject requires medical treatment excluded by the protocol or that could present a safety risk to the subject;
- The subject is not willing to continue participation in the study (withdraws consent);
- The subject experiences an increase in disease activity that requires additional or different therapy;
- The subject develops active TB or a positive response to QuantiFERON-TB Gold test anytime during the study. If the QuantiFERON-TB Gold test yields low positive results (defined as QuantiFERON TB Antigen minus Nil value = 0.35 - 2 IU/mL), a repeat test should be done. If the repeat test is negative, the patient can continue on the study, subject to the clinical judgment of the Investigator);
- The female subject becomes pregnant;
- The subject is lost to follow up;
- The subject demonstrates a consistent lack of compliance with the provisions of the protocol;
- In the opinion of the Investigator it is in the best interest of the subject to discontinue participation; or

The subject can also be discontinued if the sponsor decides to terminate the study for any reason (e.g., an unexpected SAE not previously observed with adalimumab occurs).

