4.3 Method of Assigning Subjects to Treatment Groups

Once the subject has signed the ICF at Screening, site personnel will assign a subject identification number (ID). The subject ID will include the site number (3 digits), and 3 digit subject number, assigned sequentially starting with 001. This number will be utilized to identify the subject throughout the study period. Once the subject ID has been assigned, the site will contact the Interactive Voice Response System/Interactive Web-based Response System (IXRS) to register the subject ID. Dropouts (subjects who discontinue study treatment early, and subjects who are randomized but not treated) will not be replaced. No individual is allowed to re-enter the study if previously randomized and dosed.

Subjects will be assigned to study drug in accordance with the randomization schedule generated using permuted block randomization by an independent statistician.

Approximately 500 subjects will be randomly assigned in a 1:1 ratio (approximately 250/arm) to receive 1 of the following treatments in Treatment Period 1:

- 2 SC injections (2 pre-filled syringes, [80 mg]) of Humira on Week 0/Day 0 and 1 SC injection (1 pre-filled syringe [40 mg]) of Humira QOW from Week 1/Day 7 through up to Week 15/Day 105.
- 2 SC injections (2 pre-filled syringes, [80 mg]) of CHS-1420 on Week 0/Day 0 and 1 SC injection (1 pre-filled syringe [40 mg]) of CHS-1420 QOW from Week 1/Day 7 through up to Week 15/Day 105.

Subject randomization will be stratified by body mass index (BMI) (less than ($<$) 30 kg/m² or greater than or equal to (\geq) 30 kg/m²), age (<65 yrs or ≥ 65 yrs) and region.

At the end of Treatment Period 1 (Week 16), subjects taking Humira will either begin dosing with CHS-1420 or continue with Humira during Treatment Period 2. A single randomization will be used to determine treatment in Treatment Periods 1 and 2. In effect, a 2:1:1 randomization will be used where for each 2 subjects randomized to receive CHS-1420 an additional 2 will be assigned to receive Humira in Treatment Period 1. For the subjects assigned to Humira in Treatment Period 1, 1/2 of these will be randomly assigned to continue with Humira for Treatment Period 2 and 1/2 will be assigned to switch to CHS-1420 for Treatment Period 2.

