8.3 Determination of Sample Size

Approximately 500 subjects will be randomized and treated for this trial (approximately 250 per arm in Treatment Period 1).

The sample size was determined to show comparable efficacy for the following endpoint based upon the PASI at Week 12:

- The percentages of subjects in each group, CHS-1420 and Humira, achieving PASI-75 at Week 12

For the proportion of subjects achieving a PASI-75, it has been assumed that 70% of subjects will be responders in both the reference group, Humira, and the CHS-1420 group. The sample size will produce 90% power to establish equivalence at the 5% alpha level (2-sided) with an equivalence margin of 15% (absolute). Subjects who lack a PASI assessment at Week 12 will be considered non-responders in the primary analyses.

The margin for equivalence has been based statistically on the study results from Menter (2008) and to a lesser extent Gordon (2006). At 12 weeks, Menter had PASI-75 responses of 68% (554/814) for Humira and 5% (20/398) for control. This results in a treatment effect of approximately 63% (absolute). A lower 95% confidence bound (2-sided) for the difference in response rates can be calculated to be 59%. The proposed 15% margin for demonstrating equivalence is much smaller than the demonstrated benefit associated with Humira.

Though Gordon (2006) was a considerably smaller study, at 12 weeks this study had similar PASI-75 responses of 71% (70/99) for Humira and 19% (9/48) for control. This results in a treatment effect of approximately 52% (absolute). Pooling Gordon and Menter using the method of Der Simonian and Laird, yields a lower bound on the treatment effect of at least 50% which also supports the use of a 15% equivalence margin.

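### A Week 12 PASI recorded after a switch to another psoriasis therapy can count as a PASI-75 response, and no specified primary-endpoint analysis tests the effect on the equivalence conclusion

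*Combined protocol and SAP*

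**What the plan says.** **Primary rule.** The primary analysis uses the Full Analysis Population by randomized arm (Section 8.1.2). On the decision, Section 8.2.2 says "Equivalence will be based upon the 95% (2-sided) confidence interval for the difference in PASI-75 rates", to be compared with ±15 percentage points. Its only imputation of non-response is "Subjects who lack a PASI assessment at Week 12 will be considered non-responders in the primary analyses". Its only stated sensitivity analysis substitutes the last available score.

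**Leaving study drug.** Section 3.3.4 lists, among the reasons for withdrawal from study therapy, "The subject experiences an increase in disease activity that requires additional or different therapy". Under Section 3.1, subjects who stop drug in Treatment Period 1 "will be encouraged to return for all study visits through Week 16". The Week 12 visit falls inside that window.

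**Other therapy.** Section 4.8 prohibits other systemic and biologic psoriasis treatments, phototherapy and the stronger topical steroids during the study, and has all concomitant medication recorded.

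**Per Protocol Population.** Section 8.1.4 requires 12 weeks of treatment and PASI follow-up, and no violation that could affect interpretation of the primary endpoint. Section 8.2.2 assigns no analysis to this population.

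**The concern.** Two subjects with the same treatment failure can be scored in opposite ways. One who stops drug and does not return is a non-responder. One who stops, starts another therapy and attends Week 12 is scored on a PASI that partly reflects the other drug. The plan does not say how that PASI is used, so as written it counts as observed.

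In a superiority trial this would usually be conservative. In an equivalence trial it can work the other way: if switching follows lack of efficacy, the weaker arm has more failures to convert, the observed difference shrinks, and a difference at the margin is more easily passed as equivalence. The last-available-score analysis cannot show this, because for anyone with a Week 12 PASI the last available score at Week 12 is that same PASI.

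**Working it through.** **Inputs from the plan.** About 250 per arm, 1:1 (Section 4.3). Section 8.3 says "it has been assumed that 70% of subjects will be responders in both the reference group, Humira, and the CHS-1420 group". The margin is 15 points, the interval is a two-sided 95% CI, and the stated power is 90%. No rate of stopping drug or starting another therapy is given, so every switching rate below is an assumption.

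**Step 1: reproduce the plan's figure.** Two one-sided 2.5% tests, normal approximation, unpooled variance, no stratification.
- n per arm = 2 × 0.70 × 0.30 × (1.960 + 1.645)² / 0.15² = 242.6, so 243.
- At 250 per arm, SE = √(2 × 0.21 / 250) = 0.0410, and power = 2Φ(0.15/0.0410 − 1.96) − 1 = 91.1%.

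Both agree with the stated 250 per arm and 90%.

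**Step 2: switching that follows lack of efficacy.** Let p be an arm's true response rate with switchers counted as failures, q the fraction of failures who switch and attend Week 12, and r the fraction of those who reach PASI-75.
- Observed rate = p + (1 − p)qr.
- With common q and r, observed difference = true difference × (1 − qr).
- Chance of declaring equivalence = Φ((0.15 − d)/SE − 1.96) + Φ((0.15 + d)/SE − 1.96) − 1, where d is the observed difference.

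True rates are set at the margin, 70% versus 55%, with 250 per arm:

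| q | r | Observed rates | Difference (points) | Chance of declaring equivalence |
|---|---|---|---|---|
| 0 | – | 70.0% vs 55.0% | 15.0 | 2.5% |
| 5% | 20% | 70.3% vs 55.45% | 14.85 | 2.7% |
| 10% | 30% | 70.9% vs 56.35% | 14.55 | 3.2% |
| 20% | 50% | 73.0% vs 59.5% | 13.5 | 5.5% |
| 30% | 70% | 76.3% vs 64.45% | 11.85 | 11.9% |

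Check of the last row: SE = √((0.763 × 0.237 + 0.6445 × 0.3555)/250) = 0.0405. Then (0.15 − 0.1185)/0.0405 − 1.96 = −1.18, and Φ(−1.18) is about 0.119.

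**Step 3: switching unrelated to efficacy and unbalanced.** Take 68% in both arms with switchers counted as failures. Let 10% of one arm and 2% of the other switch, with half responding. Observed rates are 68 + 5 = 73% and 68 + 1 = 69%. The difference moves from 0 to 4 points and the chance of showing equivalence is 77%. Here the effect is away from zero.

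**Step 4: does the Per Protocol Population solve it?** It removes these subjects instead of counting them. Take 70% versus 55% with 30% of failures switching in each arm. The excluded shares are 0.30 × 30% = 9% and 0.30 × 45% = 13.5%. The remaining rates are 70/91 = 76.9% and 55/86.5 = 63.6%, a difference of 13.3 points. Exclusion also shrinks the 15-point difference. Counting the switchers as non-responders returns 15.

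**Step 5: how wide should the non-responder rule be?** Suppose 5% of each arm stop for reasons unrelated to efficacy and would respond at their arm's rate. Scoring all of them as failures multiplies the difference by 0.95: 15.0 × 0.95 = 14.25 points. A rule covering everyone who stops drug would itself dilute a true difference.

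**The case against.** **The Per Protocol Population already deals with this.** Its definition does remove these subjects: stopping drug early fails the 12-week condition, and prohibited therapy is a violation that could affect the endpoint. A reader might infer from Section 8.2.2 that the plan has nothing bearing on the problem. That is too strong. What stands is that no primary-endpoint analysis is assigned to this population, and that excluding failures is not the same check as counting them (Step 4).

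**The direction is not fixed.** This is correct. A reader might infer that the rule always pulls toward equivalence. The documents do not support that: they list reasons for stopping other than worsening, and Step 3 shows movement away from zero.

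**The rates may be small.** This also stands. Return visits are only encouraged, and those who do not return are already non-responders. Within 12 weeks a subject must worsen, stop, start another drug and improve 75% from the original baseline. Section 3.2 reports 53% and 68% PASI-75 for adalimumab every other week after a full 12 weeks, and a later-started replacement has less time. The 11.9% figure is the extreme corner of the assumed range.

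**Other therapy is prohibited, and its use would be visible.** Concomitant medication and disposition are summarized (Sections 8.2.1 and 8.2.3). But prohibition does not prevent use, Section 3.3.4 itself anticipates a need for different therapy, and a summary of use does not show its effect on the confidence interval.

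**Analysing the observed outcome by randomized arm is a recognised strategy.** It is, and the primary analysis can stay as it is. The case is for a supplementary analysis.

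**Conclusion.** The gap is real and modest. As written, a treatment failure who moves to another psoriasis therapy and attends Week 12 can be a PASI-75 responder, and no specified analysis of the primary endpoint tests how much that matters. Under efficacy-driven switching at true rates of 70% versus 55%, the chance of wrongly declaring equivalence is about 3% to 12% instead of 2.5% over the main assumed range, and about 2.7% at the low setting.

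These figures rest on assumed switching and response rates that are the same fractions of failures in both arms, on 250 per arm, and on an unstratified normal approximation to the CMH-weighted interval. The documents supply none of the switching rates, so a reader should not infer that the plan's false-equivalence rate is known to be inflated to any particular value. Nor should a reader conclude that everyone who stops study drug ought to be a non-responder (Step 5).

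**What to change.** Add to Section 8.2.2, before unblinding:

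1. A supplementary analysis of PASI-75 at Week 12 with the same CMH-weighted 95% CI. Subjects who, before the Week 12 PASI, took a psoriasis therapy prohibited in Section 4.8, or stopped study drug for increased disease activity, are scored as non-responders. Subjects who stopped for other reasons and took no other psoriasis therapy keep their observed Week 12 PASI.
2. A statement that this result is reported beside the primary result.
3. A statement that the equivalence CI is also computed on the Per Protocol Population.

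**Cost.** Extra estimates to report and interpret. The data are already planned: concomitant medication (Section 4.8), dosing in the eDiary (Section 4.9) and reasons for discontinuation (Section 7). As a supplementary analysis it leaves the primary test and its power unchanged. If the rule were used in the primary analysis, with 10% of each arm affected and half of them otherwise responders, the rate would fall from 70% to 65% and power from 91.1% to 88.0%. The Per Protocol analysis would have 89.1% to 84.1% power at 70% versus 70% if 5% to 15% of subjects were excluded (237 to 212 per arm). The change concerns scoring only and alters no clinical procedure.
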